1.4.1. Nonclinical Data

1.4.1.1. Nonclinical Pharmacology

5-MeO-DMT induces behavioural responses in rats and mice which are predominantly mediated through the 5-HT_{1A} receptor, although 5-HT_{2A} receptor activation is also involved (Berendsen, 1989; Eison, 1992; Halberstadt, 2011; Krebs-Thomson, 2006; Lucki, 1984; Smith, 1986; Tricklebank, 1985). 5-MeO-DMT has also been shown to induce aggressive responses in cats and submissive gestures, hyperactivity, distancing, checking, and reduction in social grooming in monkeys (Benington, 1965; Schlemmer, 1981; 1986; Schlemmer, 1977).

In vitro receptor profiling has shown that 5-MeO-DMT has the greatest affinity for the serotonin receptor 5-HT_{1A} (K_i of 1.9 nM, several orders of magnitude higher than that for other serotonergic receptors) (Halberstadt, 2012). 5-MeO-DMT also has significant affinity for other receptors, such as dopamine (D₁ and D₃), norepinephrine (α_2), and the norepinephrine transporter (Nagai, 2007; Ray, 2010). 5-MeO-DMT has almost no effect on monoamine release and dopamine release and reuptake (Nagai, 2007).

Serotonin receptors are widely expressed across the vascular system (Ullmer, 1995), and psychedelics are known to increase breath rate, heart rate (HR), and blood pressure (BP) (Nichols, 2016). Specifically, DMT has been demonstrated to increase HR and BP in human and animal studies (Carbonaro, 2016b; Strassman, 1994). A cardiovascular study in cats (Lalley, 1982) reported that 20 to 200 µg/kg 5-MeO-DMT inhibited phrenic and sympathetic neural discharges and depressed BP within seconds after injection, with complete recovery noted after

20 minutes. Interestingly, phrenic inhibition induced by 5-MeO-DMT could be overcome by ambient heat (Lalley, 1982). That observation could be explained by the high affinity of 5-MeO-DMT for 5-HT_{1A} receptors: 5-HT_{1A} agonists decrease BP and HR via a central mechanism, by inducing peripheral vasodilation and stimulating the vagus nerve (Dabiré, 1991; Kaumann, 2006). However, it is possible that at higher doses, 5-HT_{2A} and other 5-HT receptor-mediated effects will be apparent.

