12.4 Values of potential clinical importance

A vital signs result will be considered to be of potential clinical importance (PCI) if it falls outside the relevant range below:

Vital Sign	Range
Systolic blood pressure	90–140 mm Hg
Diastolic blood pressure	40–90 mm Hg
Pulse rate	40–100 beats/min
Temperature	35.5–37.8°C

QTcF > 450 msec and increases in QTcF from baseline (Day 0, predose) of > 30 msec will be considered to be of PCI.

13 Study population

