14.8 Other safety measures

14.8.1 Vital signs

Vital signs at each planned assessment, and change in vital signs from baseline at each planned post baseline assessment, will be summarised by actual treatment.

Plots of individual systolic blood pressure, diastolic blood pressure, and pulse rate against time will be presented for both absolute values and change from baseline by actual treatment.

Vital signs data of PCI will be listed and summarised.

A separate listing of vital sign findings, classified as clinically significant by the investigator will also be provided. Frequency of clinically significant vital signs will be summarised.

The peak (maximum value across all time points for each patient) vital signs (systolic and diastolic blood pressure, and heart rate) at baseline and post dose on day 0 will be listed and summarised.

In addition, the number of patients will be summarised for peak post dose Day 0 under the following categories:

Systolic blood pressure (mmHg)	Diastolic blood pressure (mmHg)	Heart Rate (bpm)
< 130	< 80	<40
130 - 139	80 - 89	40 – 49
140 - 149	90 - 99	50 – 59
150 – 159	100 – 109	60 – 69
160 – 169	110 – 119	70 – 79

170 – 179	120 – 129	80 – 89
180 – 189	130 – 139	90 – 99
190 – 199	>= 140	100 – 109
200 – 209		110 – 119
210 – 219		>120
>= 220		

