Table 14.3.6.xx Summary of vital signs of potential clinical importance by parameter and treatment (excluding baseline time point)

Treatment	Systolic Blood Pressure (mmHg)		Diastolic Blood Pressure (mmHg)		Heart Rate (beats/min)		Temperature (C)		etc		Overall*	
	n	(%)	n	(%)	n	(%)	n	(%)	n	(%)	n	(%)
Treatment 1 (N=xx)												

Source: Listing 16.2.xx

Patients only counted once per parameter

*Patients only counted once per treatment

Programming notes: Continued with all parameters. n = total number of results for that parameter
Only include post-treatment time points

Template T_VS4

Table 14.3.6.xx Summary of post dose clinically significant vital signs

Treatment	Planned Relative Time	Clinically Significant	
		n	(%)
Treatment 1 (N=xx)	Time 1 Time 2		

Programming notes: Continued with all timepoints. n = total number of results for that parameter

Template T_VS5

Table 14.3.7.xx Summary of peak Vital Signs ranges by treatment, ranges and parameter - Day 0 post dose

	Systolic Blood Pressure (mm Hg)										
	<130	130 - 139	140 – 149	150 – 159	160 – 169 n	170 – 179	180 – 189	190 – 199	200 - 209	210 – 219	> =220
Treatment	n (%)	n (%)	n (%)	n (%)	(%)	n (%)	n (%)	n (%)	n (%)	n (%)	n (%)
Treatment 1 (N=xx)											

Source: Listing 16.2.xx

The maximum value across all time points per subject is used for analysis.

Programming notes: Continued with all variables . n = total number of results for that parameter.
Continued with all the ranges in **section 14.8.1**

Template T_VS6

Table 14.3.6.xx Summary of peak vital signs by treatment and parameter - baseline and Day 0 post dose

Variable (units)	Treatment	Planned Relative Time	n	Mean	SD	Median	Min	Max
Systolic Blood Pressure (mmHg)	Treatment 1 (N=xx)	Predose Day 0, Postdose						

Source: Listing 16.2.xx

Programming notes: Continued with DBP and HR. The maximum value across all time points per subject are used for analysis.

Template T_EG2

Table 14.3.7.xx Summary of ECG values

Variable (units)	Treatment	Planned Relative							Change from Baseline					
		Time	n	Mean	SD	Median	Min	Max	n	Mean	SD	Median	Min	Max
Heart Rate (bpm)	Treatment 1 (N=xx)													
PR Interval (msec)	Treatment 1 (N=xx)													

Source: Listing 16.2.xx

Programming notes: Continued with all time points
Do not summarise RR or QRS axis

Template T_EG3

Table 14.3.7.xx Summary of QTcF values and changes in QTcF values of potential clinical importance

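### The Day 0 vital-sign classes use only each patient's maximum and the PCI tables pool low with high values, so no planned vital-sign frequency table counts a transient post-dose fall as a fall

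*SAP*

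**What the plan says.** **Peak tables.** SAP 14.8.1 lists and summarises "The peak (maximum value across all time points for each patient) vital signs" at baseline and after dosing on Day 0. It adds that "the number of patients will be summarised for peak post dose Day 0 under the following categories". The lowest blood-pressure classes are below 130 mmHg systolic and below 80 mmHg diastolic. The heart-rate classes go down to 50–59, 40–49 and below 40 bpm. The footnote to T_VS5 (the classes) reads "The maximum value across all time points per subject is used for analysis", and the programming note to T_VS6 (the summary) reads "Continued with DBP and HR. The maximum value across all time points per subject are used for analysis". Neither shell has a minimum.

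**PCI tables.** Under SAP 12.4 a vital-sign result "will be considered to be of potential clinical importance (PCI) if it falls outside the relevant range below". The ranges are 90–140 mmHg systolic, 40–90 mmHg diastolic and, for pulse, "40–100 beats/min". T_VS2 (by time point) and T_VS3 (all post-treatment times, each patient once per parameter) show a single n (%) per parameter.

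**Background.** Protocol 1.4.1.1 reports a fall in blood pressure in cats and offers the drug's high 5-HT1A affinity as a possible explanation, because 5-HT1A "agonists decrease BP and HR via a central mechanism, by inducing peripheral vasodilation and stimulating the vagus nerve". The potential risks in Protocol 1.6 name tachycardia and raised blood pressure, not falls.

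**The concern.** Safety is the primary objective, and the vital signs scheduled from 10 minutes after dosing are the main numerical record of the acute cardiovascular response. A maximum can show only how high a patient went. The heart-rate classes nevertheless extend below 40 bpm, so a reader who sees zeros there may conclude that nobody had a low reading, when the table shows only that nobody's highest reading was low.

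The PCI tables are the only other vital-sign frequency tables with fixed limits. They do register a low value, but in the same cell as a high one. If rises are the more common response, as the BPL-002 events in Protocol 1.4.2.2 suggest (increased systolic pressure was the most frequently reported event and increased heart rate was also among the most frequent), a pooled count would consist mostly of highs and could not show whether any lows were among them.

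**Working it through.** The SAP gives no figure to reproduce. The check applies its own rules to invented readings.

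**Inputs.** Post-dose times from Protocol 10.1.2 and the Schedule of Events: 10, 20, 30, 40, 60, 90, 120, 150, 180, 210 and 240 minutes, which is 11 readings. Classes from SAP 14.8.1; limits from SAP 12.4.

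**Invented heart-rate series (bpm, in time order)**
- A, fall only: 68, 36, 38, 52, 66, 70, 70, 69, 70, 70, 71
- B, rise only: 72, 80, 95, 104, 98, 85, 78, 74, 72, 71, 71
- C, both: 72, 104, 38, 60, then 70 throughout
- D, flat: 70 throughout

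**Step 1: class of the maximum (T_VS5).**

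| Patient | Maximum | Class | Minimum |
|---|---|---|---|
| A | 71 | 70–79 | 36 |
| B | 104 | 100–109 | 71 |
| C | 104 | 100–109 | 38 |
| D | 70 | 70–79 | 70 |

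A cannot be told from D, nor C from B. The classes below 60 bpm are empty although two of the four patients went below 40.

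**Step 2: the same for systolic pressure.** An invented series that falls to 82 mmHg and peaks at 121 is classed below 130. So is one that stays between 118 and 122.

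**Step 3: PCI by time point (T_VS2), limits 40 and 100 bpm.**
- 20 min: A (36) and C (104) are outside, so n = 2: one low, one high.
- 30 min: A (38) and C (38) are outside, so n = 2: both low.
- 40 min: only B (104) is outside, so n = 1: high.

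The cells at 20 and 30 minutes are identical but mean different things.

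**Step 4: PCI per patient (T_VS3).** Pooled count = above + below − both. Here above = 2 (B, C), below = 2 (A, C) and both = 1 (C), so the table shows 2 + 2 − 1 = 3. Without the split, a pooled 3 is compatible with anything from 0 to 3 patients with a low value.

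**Step 5: does T_VS1 supply the count?** It gives the minimum at each time point. At 30 minutes that minimum is 38, whether one patient or two are below 40. It shows how low, not how many.

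**Step 6: does T_VS4 supply it?** That shell counts investigator-judged clinically significant results by time point, with no column for parameter or direction. It includes a significant low value but does not identify it as low.

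**The case against.** The strongest reply is that nothing is lost. Falls appear in the T_VS1 minima and changes from baseline, in the individual plots of pressure and pulse, and in the PCI listing, which prints the value and so shows direction. Hypotension or bradycardia reported as an adverse event is tabulated by preferred term. Telemetry to 90 minutes adds a further source. With at most 12 patients, anyone can count lows by hand. A peak table that grades rises also matches the risks named in Protocol 1.6, and Protocol 1.4.2.3.1 reports no clinically important vital-sign changes in the BPL-003 healthy-volunteer study. All of this stands, and it limits the weight of the point. It does not supply a tabulated count of patients with a low value.

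Three stronger readings are tempting, and the documents do not support them.

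- **That bradycardia can never reach the low heart-rate classes.** A steadily low rate does reach them. Assume independent normal readings with a within-person SD of 6 bpm (an assumption; the documents give none). The chance that all 11 readings are below 60 is Φ((60 − true rate)/6)^11. At a true rate of 55 this is Φ(0.83)^11, about 8%; at 50 it is Φ(1.67)^11, about 58%. Protocol 10.1.2 also allows readings to stop once readiness for discharge is confirmed, which makes a low maximum easier to obtain. Only a transient fall is bound to be missed.
- **That the primary endpoint is compromised.** It is the percentage of patients with clinically significant abnormal post-dose vital signs, as judged by the investigator. It has no direction and counts a significant low value.
- **That the protocol predicts falls in these patients.** Section 1.4.1.1 offers a possible mechanism for an animal finding. It also says psychedelics are known to raise heart rate and blood pressure.

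**Conclusion.** The point holds as a gap in tabulation. T_VS5 and T_VS6 describe only the upper end of each patient's Day 0 readings. T_VS2 and T_VS3 register low values but merge them with high ones, and T_VS4 carries no direction. No planned vital-sign frequency table therefore gives the number of patients whose pressure or heart rate fell below the SAP's limits. This follows from the text and shells and needs no distributional assumption; the series above only illustrate it.

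The size is modest: no data are lost, no endpoint is misestimated, and the group is small enough to check by hand. The gain is a correct tabulated count by direction. The change is worth making because the SAP already defines the lower limits and the readings are already scheduled.

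**What to change.** Before database lock, amend SAP 14.8.1 and the shells:

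1. **T_VS2 and T_VS3:** for each parameter, report below-range and above-range counts in separate columns, using the SAP 12.4 limits. A patient with both appears in both columns; the overall column in T_VS3 can stay.
2. **T_VS6:** add each patient's Day 0 post-dose minimum for systolic pressure, diastolic pressure and heart rate beside the peak.
3. **T_VS5:** apply the existing heart-rate classes (below 40, 40–49, 50–59) to that minimum, and count patients with a minimum systolic pressure below 90 mmHg and a minimum diastolic pressure below 40 mmHg. Label clearly which rows use the maximum and which the minimum.
4. **Listing 16.2.9.3,** the source for T_VS5 and T_VS6, currently carries only maxima and needs the minimum as well.

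The cost is a few more columns and rows and the programming for them. No new assessments or thresholds are needed.

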10.1.2. Vital Signs

Vital sign measurements (HR, systolic and diastolic BP) and temperature must be collected at each visit outlined in the Schedule of Events ([Table 1](#)). The baseline will be measured in triplicate within 30 min (+/- 5mins) before dosing, (Triplicate measurements should be obtained as closely as possible in succession, and no more than 2 min apart; temperature does not need to be repeated in triplicate). Predose BP must be within normal range pre dose on dosing day and if not then repeated ~ 1 h later .

Vital signs then taken as single measurements at 10, 20, 30, 40 mins, and then every 30 min (+/- 5mins) from 1 hour post-dose until 4 hours post dose: and when the patient is assessed as ready to be discharged on Day 0, if later than 4 h post dose. BP should be measured in the supine position under standardised conditions. A note should be taken of any movement of the participant during blood pressure measurements. If systolic blood pressure is > 160 mmHg then repeat the measurement. Vital signs from 90 min post-dose onwards will form part of the readiness for discharge questionnaire and can be stopped once the patients are confirmed ready for discharge as per the questionnaire.

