11.2 Conventions for summary statistics and data displays

The minimum set of summary statistics for numeric variables will be: n, mean, standard deviation (SD) (or standard error), median, minimum, and maximum. 95% confidence intervals (CI) will be presented where appropriate for data interpretation.

Categorical data will be summarised in frequency tables with n and percentage. Summaries of a categorical variable will include all recorded values.

The minimum and maximum values will be presented with the same number of decimal places as the raw data collected on the case report form (CRF) (or to 3 significant figures for derived parameters less than 100 and as integers for values more than 99). The mean and percentiles (eg median) will be presented using one additional decimal place. The standard deviation and standard error will be presented using two additional decimal places.

12 Data handling conventions

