14.8.2 ECG

QT interval data will be presented using Fridericia's (QTcF) corrections.

ECG variables will be summarised by treatment and time point. Differences from baseline (Day 0, predose) will be summarised by treatment and time point.

Plots of individual QTcF against time will be presented for both absolute values and change from baseline by actual treatment.

The number of patients with a potentially clinically important QTcF value will be summarised by actual treatment and time point, giving the numbers of patients with QTcF > 450 msec, > 480 msec and > 500 msec, and the numbers of patients with increases in QTcF from baseline of > 30 msec and > 60 msec³. A supporting listing of all patients with a QTcF value of PCI and a separate listing of ECG findings classified as abnormal by the investigator will also be provided.

The frequency of clinically significant ECG values will be summarised.

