Treatment	Planned Relative Time	451 – 480 msec		481 – 500 msec		> 500 msec		>30-60 msec Increase		>60 msec Increase	
		n	(%)	n	(%)	n	(%)	n	(%)	n	(%)
Treatment 1 (N=xx)	Time 1										
	Time 2										
	Time 3										

Source: Listing 16.2.xx

Programming notes: Continued with all time points. n = total number of results for that parameter

Template T_EG5

Table 14.3.7.xx Summary of clinically significant ECG values

Treatment	Planned Relative Time	Abnormal CS	
		n	(%)
Treatment 1 (N=xx)	Time 1		
	Time 2		

Source: Listing 16.2.xx

Programming notes: Continued with all timepoints. n = total number of results for that parameter
For cardiac telemetry, change planned relative time to Start and End date/time

Template T_RDQ

Table 14.3.7.xx Summary of readiness of discharge questionnaire (RDQ)- Time to discharge (units)

Treatment	Planned Relative Time	n	Mean	Median	Min	Max
Treatment 1 (N=xx)						

Source: Listing 16.2.xx

Programming notes: Continued with all time points

Template T_ReAQ_PG _

Table 14.3.8.xx Summary of re-activation questionnaire (ReAQ)

Assessment	Planned Relative Time	Treatment 1 (N=xx)
Number of Patients with Re-activation (%)	Time 1	Yes
		No
Number of Days after dose (Days)	Time 1	n
		Mean
		SD
		Median
		Min
		Max
Number of Re-activation events	Time 1	n
		Mean
		SD
		Median
		Min
		Max
Emotional Valence	Time 1	Mostly Positive
		Neutral
		Mostly Negative
Functional Impact- Work (%)	Time 1	None
		Mild
		Moderate
		Severe
Functional Impact- Social Life (%)	Time 2	
	Time 1	None
		Mild
		Moderate
		Severe
	Time 2	

Functional Impact- Family Life (%)	Time 1	None Mild Moderate Severe
<hr/>		

[figure not shown]
Source: Listing 16.2.xx

Programming notes: *Continued with all assessments and timepoints. Occurrence =Number of patients with Re-activation).*
Denominator for percentages will be total number of scores recorded (excluding N/A) at relative time point

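### The SAP's peak heart-rate classes omit exactly 120 bpm, and the QTcF table shell uses separate bins where the text asks for cumulative counts

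*SAP*

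**What the plan says.** **Peak vital signs.** SAP 14.8.1 takes each patient's maximum systolic pressure, diastolic pressure and heart rate after dosing on Day 0, and states that "the number of patients will be summarised for peak post dose Day 0 under the following categories". The last two classes in each column are:

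- systolic: 210–219, then >= 220
- diastolic: 130–139, then >= 140
- heart rate: 110–119, then >120

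Shell T_VS5 in SAP 19.2.1, which produces Table 14.3.6.5, imports these classes. Its programming note reads "Continued with all the ranges in" that section.

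**QTcF.** SAP 12.4 defines potential clinical importance (PCI): "QTcF > 450 msec and increases in QTcF from baseline (Day 0, predose) of > 30 msec will be considered to be of PCI". SAP 14.8.2 then asks for a summary by treatment and time point, "giving the numbers of patients with QTcF > 450 msec, > 480 msec and > 500 msec", and the numbers with "increases in QTcF from baseline of > 30 msec and > 60 msec". Protocol 11.7.1.3 asks for the same five counts. Shell T_EG3, which produces Table 14.3.7.2, has columns headed 451–480, 481–500 and > 500 msec, then ">30-60 msec Increase" and >60 msec.

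SAP section 17, which lists changes from the protocol analysis, mentions only laboratory flagging. SAP 19.1 ranks its contents table above the shells for numbering, but nothing says whether text or shell prevails on content.

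**The concern.** A set of classes for a frequency table should be exhaustive and should count what the text defines. The heart-rate classes fail the first requirement at one attainable value. The programmer must then either leave that patient out, so that the row does not add to N, or depart silently from the SAP.

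The QTcF shell fails the second requirement. The text's thresholds are cumulative and the shell's are not, so the two instructions give different numbers under the same table title. Whether any value also drops out depends on whether QTcF is rounded before it is classified, which the SAP does not say.

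Both tables serve the safety and tolerability objective, and Protocol 1.6 names tachycardia among the potential risks. It is therefore worth having the classes right before programming.

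**Working it through.** There is no power or sample-size figure to reproduce. The check codes each class as written and looks for values that belong to none.

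**1. Heart rate.** Protocol 10.1.2 has "Vital signs then taken as single measurements at 10, 20, 30, 40 mins" and then every 30 minutes from 1 hour. Post-dose values are thus single readings, not means; I assume they are recorded as whole numbers.

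| Variable | Range tested (whole units) | Values in no class |
|---|---|---|
| Heart rate, as written | 20–220 bpm | 120 only |
| Systolic, as written | 60–260 mmHg | none |
| Diastolic, as written | 30–180 mmHg | none |
| Heart rate, top class >=120 | 20–220 bpm | none |

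With 12 patients, one unclassified patient is 1/12 = 8.3 percentage points of the row.

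**2. QTcF, whole numbers.** Take three patients at one time point with 452, 485 and 510 msec.

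- Text: above 450, 3; above 480, 2; above 500, 1.
- Shell: 451–480, 1; 481–500, 1; above 500, 1.
- Adding shell columns: 1 + 1 + 1 = 3; 1 + 1 = 2; 1. The text's counts are recovered, and no whole number above 450 lacks a column.

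**3. QTcF, unrounded.** On a 0.1 msec grid above 450, the values in no shell column are 450.1 to 450.9 and 480.1 to 480.9. Take 450.4, 480.4 and 505.0.

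- Text: 3, 2, 1.
- Shell, unrounded: 0, 0, 1. Adding columns gives 1, 1, 1, so two patients who meet the PCI rule are missing.
- Shell after rounding to 450, 480 and 505: 1, 0, 1. Adding columns gives 2, 1, 1. This still differs from the text's counts on the unrounded values, and agrees only if the PCI rule is applied to the rounded values too (450 is not above 450, and 480 is not above 480).

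So what matters is that the flag and the table use the same value.

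**4. Can QTcF be fractional?** Fridericia's formula is QTcF = QT / (60/HR)^(1/3). For QT 390 msec and heart rate 63 bpm, the result is 390 / (60/63)^(1/3) = 396.39 msec. A derived value is therefore generally not a whole number. The SAP's only rounding convention, in 11.2, presents minima and maxima as in the raw data, "or to 3 significant figures for derived parameters less than 100 and as integers for values more than 99". It governs presentation, not classification.

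**5. Change in QTcF.** The columns >30–60 and >60 have no gap. For increases of 32 and 65 msec the text gives 2 and 1 and the shell gives 1 and 1; adding columns gives 1 + 1 = 2.

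**The case against.** The strongest reply is that little or no information is lost. A heart rate of 120 bpm lies outside the 40–100 range in SAP 12.4. The patient therefore appears in the PCI listing (16.2.9.1) and the PCI tables (14.3.6.2 and 14.3.6.3). The peak itself is in Listing 16.2.9.3 and contributes to Table 14.3.6.6. A QTcF of 450.5 msec would likewise appear in Listing 16.2.9.4. All of this stands. A reader might infer that patients at a safety boundary vanish from the report; the documents do not support that, because only one cell of one descriptive table is affected in each case.

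It is also fair to say that disjoint QTcF bins are a layout choice when values are whole numbers, and that the columns are labelled clearly enough that few would read 451–480 as everyone above 450. Nor does T_EG3 ever add to N, since it has no column for 450 and below; that argument applies to the heart-rate table alone.

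The fractional gap is conditional. The documents do not say that QTcF is classified unrounded. The listing shell's sample row, with an observed 396 and a change of -6.5, is placeholder data and shows nothing about this trial's precision.

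Finally, the missing equals sign may be a typographical slip or a lost character. The neighbouring cells in the same table keep theirs, so a lost character is speculation, and a slip still needs correcting because T_VS5 reuses it.

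**Conclusion.** Both specifications are wrong as written, and the consequence is minor.

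- **Heart rate:** exactly one whole-number value, 120 bpm, has no class in Table 14.3.6.5. This assumes whole-number recording.
- **QTcF:** the shell's columns are not the five counts that SAP 14.8.2 and Protocol 11.7.1.3 require, and the difference is not declared in SAP section 17. With whole-number values the required counts follow by addition. With unrounded values, the intervals 450–451 and 480–481 (end points excluded) meet the PCI rule but have no column, so the table can disagree with its own supporting listing.

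It would go too far to say that QTcF values will be lost: that needs unrounded classification, which the SAP neither states nor excludes. Nor can a probability be attached to either gap from the documents, which give no heart-rate or QTcF distribution for these patients. The study is descriptive, tests no hypothesis and has at most 12 patients, whose individual values are listed, so no conclusion turns on this.

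**What to change.** 1. In SAP 14.8.1, change the top heart-rate class from >120 to >=120. T_VS5 then inherits it.
2. In T_EG3, replace the columns with the cumulative >450, >480, >500, >30 and >60 msec of SAP 14.8.2. Alternatively, keep disjoint bins as >450–480, >480–500 and >500 with a >450 total, and >30–60 and >60 with a >30 total.
3. State that these columns are applied to the same QTcF value, at the same precision, as the PCI flag in SAP 12.4.

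The cost is a few edits to class limits and one sentence in the SAP. No new data are needed, and nothing in the conduct of the trial changes.
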